6.3 Determination of Sample Size

Since the primary endpoint is PFS, the reference median PFS for vorinostat is assumed to be 169 days.⁵ The median PFS for KW-0761 therapy is targeted for 254 days, a 50% improvement over this reference median. For a 24-month accrual and 12 month follow-up on the last subject dosed, Table 10.3-1 of the protocol gives the power and the number of PFS events required to show superior PFS for KW-0761 therapy over vorinostat at the one-sided

0.025 significance level. The Intent-to-Treat (ITT) set is used for this primary analysis. The same analysis conducted using the Efficacy Evaluable set is considered secondary.

Under these assumptions, for the ITT population, a total of 255 PFS events will give 90% power. For this study, the final primary analysis comparing PFS between treatment groups will not be conducted until 255 PFS events occur or until a maximum of 24 months after the last randomized subject's first dose, whichever comes first. In the event that the study is stopped prior to 255 PFS events being observed, the primary test will be performed at less than 90% power under the current assumptions according to Table 10.3-1 in the protocol.

Each of these calculations used a log-rank test to compare the two survival curves. Sample size calculations were computed using SAS software version 9.3 using PROC POWER, Twosamplesurvival test = logrank.

The total sample size of 288 represents the approximate number of subjects that may be necessary for 255 PFS events to occur within the projected 36 months of the trial. If a 10% inflation factor is applied to this total (about 29 subjects) to take into account those subjects that may be lost to follow-up prior to documented progression, a total of 317 enrolled subjects may be necessary in order to observe 255 PFS events.

The observed rates of PFS events, recruitment, and drop-outs will be monitored throughout the study and may be used to alter the number of sites, the accrual period, and the follow-up period to achieve the required 255 PFS events in a timely manner. If the 255 PFS events are not observed within 36 months from the start of enrollment the study will be stopped at approximately 24 months after the last randomized subject's first dose.

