6.12.1 Adverse Events

For subjects in the KW-0761 arm and subjects in the vorinostat arm who do not cross over to KW-0761, treatment-emergent adverse events (TEAEs) during the randomized treatment period are defined as adverse events with an onset date/time after the first dose of randomized study drug until 90 days after the last dose of randomized study drug or initiation of an alternative therapy whichever comes first.

For subjects in the vorinostat arm who cross over to KW-0761 treatment arm, TEAEs during the randomized treatment period are defined as adverse events with an onset date/time after the first dose of randomized study drug and prior to the start of KW-0761. An adverse event with onset date/time after the start of KW-0761 will also be considered as a TEAE during the randomized treatment period if it is considered related to vorinostat. TEAEs during the crossover portion are defined as adverse events with an onset date/time after the first dose of KW-0761 and within 90 days after the last dose of KW-0761 or initiation of an alternative therapy whichever comes first.

TEAEs during the randomized treatment period will be summarized by treatment arm and in total based on the Safety Analysis Set. For subjects who are initially assigned to vorinostat arm and are crossed over to KW-0761 arm, TEAEs during the crossover portion will be summarized separately. A drug-related AE is defined as any event with a relationship to study drug recorded as “definitely”, “probably” or “possibly”. Any adverse events for which relationship to study drug are not recorded will be assumed to be probable.

An overview of adverse events for the randomized treatment period will be provided which summarizes the subject incidence of the following information:

- Any AEs,
- Any TEAEs,
- Drug-related TEAEs,
- NCI/CTCAE grade III/IV/V AEs,
- NCI/CTCAE grade III/IV/V TEAEs,
- Drug-related NCI/CTCAE grade III/IV/V TEAEs,
- Deaths,
- Serious AEs,
- Treatment-emergent SAEs,
- Drug-related treatment-emergent SAEs,
- Discontinuation due to AEs,
- Discontinuation due to TEAEs, and

- Discontinuation due to drug-related TEAEs.

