The number and percentage of subjects with TEAEs during the randomized treatment period will be summarized for each treatment arm and in total by system organ class (SOC) and preferred term. Drug-related TEAEs, grade III/IV/V TEAEs, and drug-related grade III/IV/V TEAEs, treatment-emergent SAEs, drug-related treatment-emergent SAEs, TEAEs leading to discontinuation of study drug, and drug-related TEAEs leading to discontinuation of study drug will be summarized in the same manner. For these summaries, subjects with multiple adverse events will be counted only once per SOC and preferred term.

In addition, summaries will be provided for the number and percentage of subjects with TEAEs and drug-related TEAEs by SOC and preferred term and by the highest NCI CTCAE grade. For these summaries, subjects with multiple adverse events will be counted only once by the highest NCI CTCAE grade within an SOC and preferred term.

Adverse events during the crossover portion that are related to KW-0761 will be summarized separately in the same manner as described above for subjects who are randomized to vorinostat arm and then crossed over to KW-0761 treatment. Another summary of adverse events related to Vorinostat may be presented if necessary.

A summary will be provided for the number and percentage of subjects with TEAEs related to KW-0761 by SOC and preferred term for all subjects exposed to KW-0761 and separately for subjects who are initially randomized to KW-0761 and for subjects who are crossed over to KW-0761 treatment.

The number and percentage of subjects with TEAEs during the randomized treatment period will also be summarized for each treatment arm and in total by system organ class (SOC) and preferred term for the following subgroups: Gender and Age (< 65 years vs \geq 65 years).

In addition to the summaries described above, exposure-adjusted incidence rate and exposure-adjusted event rate will be summarized for each treatment arm and in total by preferred term for the following special TEAEs (system organ class):

- Infections and infestations,
- Respiratory, thoracic and mediastinal disorders,
- Renal and urinary disorders,
- Musculoskeletal and connective tissue disorders.

The exposure-adjusted incidence rate per patient-months of exposure will be calculated as (the number of patients with AEs/sum of days at risk for AEs) * 30.42 days/month; the

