<<Programming Note: For Table 14.3.2.1 to 14.3.2.6, only display the total column.>>

Table 14.3.3.1
 Number (%) of Subjects with Treatment-Emergent Adverse Events (TEAEs) Related to KW-0761 for Subjects Exposed to KW-0761
 By System Organ Class and Preferred Term
 Safety Analysis Set

System Organ Class* Preferred Term*	Initially Randomized to KW-0761 N=xx		Crossed Over to KW-0761** N=xx		All Subjects Exposed to KW-0761** N=xx	
	n	(%)	n	(%)	n	(%)
Subjects with Any TEAEs	xx	(xx.x)	xx	(xx.x)	xx	(xx.x)
System Organ Class 1	xx	(xx.x)	xx	(xx.x)	xx	(xx.x)
Preferred Term 1	xx	(xx.x)	xx	(xx.x)	xx	(xx.x)
Preferred Term 2	xx	(xx.x)	xx	(xx.x)	xx	(xx.x)
System Organ Class 1	xx	(xx.x)	xx	(xx.x)	xx	(xx.x)
Preferred Term 1	xx	(xx.x)	xx	(xx.x)	xx	(xx.x)
Preferred Term 2	xx	(xx.x)	xx	(xx.x)	xx	(xx.x)
Etc. ...						

Note: Percentage is calculated using the number of subjects in the column heading as the denominator.

* MedDRA Version 15.1 was used for coding.

** For subjects who are randomized to Vorinostat and crossed over to KW-0761, the TEAEs during the crossover portion are summarized.

Table 14.3.3.2
 Exposure-Adjusted Incidence Rate of Infections and Infestations During Randomized Treatment Period
 By Preferred Term
 Safety Analysis Set

System Organ Class* Preferred Term*	Number(%) of AE		Incidence Rates Per Patient-months of Exposure[a]	
	Vorinostat N=xx n (%)	KW-0761 N=xx n (%)	Vorinostat #.#	KW-0761 #.#
INFECTIONS AND INFESTATIONS	xx (xx.x)	xx (xx.x)	#.#	#.#
Preferred Term 1	xx (xx.x)	xx (xx.x)	#.#	#.#
Preferred Term 2				
Preferred Term 3				
Etc.				

Percentage is calculated using the number of subjects in the column heading as the denominator.

If a subject experienced more than one adverse event within an SOC, the subject will be counted once for that SOC. If a subject experienced more than one adverse event within a preferred term, the subject will be counted once for that preferred term.

* MedDRA Version xx.x was used for coding.

[a] Incidence Rates per Patient-months of Exposure = (Number of patients with AEs/sum of days at risk for AEs) * 30.42 days/month, where days at risk is defined as the last dose date of randomized treatment - first dose date of randomized treatment + 90 for subjects who did not crossover and first dose date of KW-0761 - first dose date of randomized treatment for subjects who crossed over.

Table 14.3.3.3
 Exposure-Adjusted Event Rate of Infections and Infestations During Randomized Treatment Period
 By Preferred Term

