 Safety Analysis Set

System Organ Class* Preferred Term*	Number(%) of AE		Event Rates Per Patient-months of Exposure[a]	
	Vorinostat		KW-0761	
	N=xx n (%)	N=xx n (%)	Vorinostat #.#	KW-0761 #.#
INFECTIONS AND INFESTATIONS	xx (xx.x)	xx (xx.x)	#.#	#.#
Preferred Term 1	xx (xx.x)	xx (xx.x)	#.#	#.#
Preferred Term 2				
Preferred Term 3				
Etc.				

Percentage is calculated using the number of subjects in the column heading as the denominator.

If a subject experienced more than one adverse event within an SOC, the subject will be counted once for that SOC. If a subject experienced more than one adverse event within a preferred term, the subject will be counted once for that preferred term.

* MedDRA Version xx.x was used for coding.

[a] Event Rates per Patient-months of Exposure = (Number of AEs/sum of days at risk for AEs) * 30.42 days/month, where days at risk is defined as the last dose date of randomized treatment - first dose date of randomized treatment + 90 for subjects who did not crossover and first dose date of KW-0761 - first dose date of randomized treatment for subjects who crossed over.

The following tables will have similar layout as Table 14.3.3.2 and Table 14.3.3.3:

Table 14.3.3.4
Exposure-Adjusted Incidence Rate of Respiratory, Thoracic and Mediastinal Disorders During Randomized Treatment Period
By Preferred Term
Safety Analysis Set

Table 14.3.3.5
Exposure-Adjusted Event Rate of Respiratory, Thoracic and Mediastinal Disorders During Randomized Treatment Period
By Preferred Term
Safety Analysis Set

Table 14.3.3.6
Exposure-Adjusted Incidence Rate of Renal and Urinary Disorders During Randomized Treatment Period
By Preferred Term
Safety Analysis Set

Table 14.3.3.7
Exposure-Adjusted Event Rate of Renal and Urinary Disorders During Randomized Treatment Period
By Preferred Term
Safety Analysis Set

Table 14.3.3.8
Exposure-Adjusted Incidence Rate of Musculoskeletal and Connective Tissue Disorders During Randomized Treatment Period
By Preferred Term
Safety Analysis Set

Table 14.3.3.9
Exposure-Adjusted Event Rate of Musculoskeletal and Connective Tissue During Randomized Treatment Period
By Preferred Term
Safety Analysis Set

Table 14.3.4.1
 Shift Table for Selected Laboratory Parameters During Randomized Treatment Period - Serum Chemistry
 Safety Analysis Set

Parameter (Unit) Treatment Arm	N'	Baseline	---- Highest CTCAE Grade During Randomized Treatment Period ----		
			<=Grade II	>=Grade III	Total
XXX (Unit)					

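### Days at risk in the exposure-adjusted AE tables do not match the TEAE counting window, and the incidence tables keep adding time after a subject's first event

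*SAP*

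**What the plan says.** SAP 6.12.1 plans an exposure-adjusted incidence rate and an exposure-adjusted event rate, by arm and preferred term, for TEAEs in four system organ classes. Incidence appears in Tables 14.3.3.2, .4, .6 and .8, and event rates in .3, .5, .7 and .9.

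**Denominator, both rates (footnote [a]).** For subjects who did not cross over: "where days at risk is defined as the last dose date of randomized treatment - first dose date of randomized treatment + 90". For the others: "first dose date of KW-0761 - first dose date of randomized treatment for subjects who crossed over".

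**Numerator window (SAP 6.12.1).** For subjects who do not cross over, TEAEs are counted "until 90 days after the last dose of randomized study drug or initiation of an alternative therapy whichever comes first". Protocol 7.1 ends AE collection at the same point. For crossovers, the main rule stops at the start of KW-0761, but an AE that begins later "will also be considered as a TEAE during the randomized treatment period if it is considered related to vorinostat".

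**Formulas.** The incidence rate takes "the number of patients with AEs/sum of days at risk for AEs) * 30.42 days/month". Its table note says: "If a subject experienced more than one adverse event within an SOC, the subject will be counted once for that SOC". The other tables use: "Event Rates per Patient-months of Exposure = (Number of AEs/sum of days at risk for AEs) * 30.42 days/month".

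**The concern.** A rate per unit of exposure is meaningful only if the events and the time come from the same window. Two things break that here.

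**Window mismatch (both rates).** Every subject who did not cross over receives a flat 90 days after last dose. If alternative therapy, death or data cutoff comes sooner, part of that time cannot yield a countable event, and the rate is too low. Protocol 7.7 provides for subjects still on treatment at the primary analysis, so for them the added days can lie wholly beyond the data. For crossovers the error runs the other way: late vorinostat-related events enter the numerator after the denominator has closed.

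**No stop at first event (incidence only).** A subject who already has the event can no longer add to the numerator, but keeps adding time. The rate therefore falls as exposure lengthens. That is the dependence an exposure adjustment should remove, and the design itself expects longer PFS on KW-0761.

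A reader comparing infection or respiratory incidence between arms could see a difference that comes only from the arithmetic. If KW-0761 is given for longer, that artefact favours KW-0761.

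**Working it through.** The table shells are blank, so there is no planned rate to reproduce. The conversion constant is sound: 365/12 = 30.42 days per month.

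**Inputs from the documents**
- Median PFS 169 days (vorinostat) and 254 days (KW-0761), SAP 6.3. Using these for time on treatment is an assumption.
- 24 months' accrual and a 36-month projected trial, SAP 6.3: "For a 24-month accrual and 12 month follow-up on the last subject dosed".
- At least 14 days from last vorinostat dose to first KW-0761 dose, Protocol 5.3.

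**Assumptions, not in the documents**
- Exponential treatment times and a constant AE hazard, equal in both arms, so the true ratio is 1.00.
- A share *c* of vorinostat subjects crosses over.
- A share *a* of subjects who do not cross over starts alternative therapy 30 days after last dose.

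Mean time on treatment is median/ln 2: 254/0.693 = 366 days and 169/0.693 = 244 days.

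**One subject, alternative therapy at day 30**
- 169 days on drug: footnote 169 + 90 = 259; counting window 169 + 30 = 199. Excess 30%.
- 254 days on drug: 344 against 284. Excess 21%.
- No early stop: excess zero.

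**Window mismatch alone.** The event-rate ratio equals (counted days/footnote days) for KW-0761 divided by the same quantity for vorinostat. Mean footnote days are 366 + 90 = 456 for KW-0761. For vorinostat they are 244 + 90 = 334 without crossover and 244 + 14 = 258 with it, so 334 − 76*c* overall. An alternative-therapy start at day 30 removes 90 − 30 = 60 days. With *a* = 0.5 in both arms and no cutoff, KW-0761 gives 426/456 = 0.934, and:

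| Crossover | Vorinostat counted/footnote days | Event-rate ratio |
|---|---|---|
| 0% | 304/334 = 0.910 | 1.03 |
| 50% | 281/296 = 0.949 | 0.98 |
| 90% | 262/265 = 0.989 | 0.95 |

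With equal *a* in both arms, the ratio is 1 when 334 − 76*c* = 456(1 − *c*), that is *c* = 122/380 = 0.32.

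Uniform 24-month accrual with a month-36 cutoff leaves 16% of KW-0761 and 7% of vorinostat subjects on treatment. The cutoff alone then gives a ratio of 0.98. Over all scenarios tested, including unequal alternative-therapy shares (0.3 against 0.8, both ways round), the ratio ran from 0.89 to 1.12. In a separate set of runs without a cutoff (crossover 0, 50 or 70%; *a* 0, 50 or 80%), each arm's own rate was understated by 0–15%.

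**Late vorinostat-related events.** At 0.05 per month over 258 days, a crossover subject expects 0.05 × 258/30.42 = 0.424 events. If 5% of crossovers have one late event, the crossover count rises by 0.05/0.424 = 12% with no added time. At 0.02 per month the expected count is 0.170 and the rise is about 30%.

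**No stop at first event, windows otherwise matched.** With daily hazard λ and mean treatment time *m*, the share with an event is 1 − exp(−90λ)/(1 + λ*m*), and the planned rate is that share × 30.42/(*m* + 90). At 0.05 per month, λ = 0.05/30.42 = 0.00164:
- KW-0761: share 0.462; 0.462 × 30.42/456 = 0.031 per month.
- Vorinostat: share 0.384; 0.384 × 30.42/334 = 0.035 per month.
- Ratio 0.88, although both true rates are 0.050.

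Simulated ranges over the scenarios (400,000 subjects per arm; the milder ends apply the accrual pattern and the month-36 cutoff):

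| True hazard per month | Incidence ratio |
|---|---|
| 0.005 | 0.98–0.99 |
| 0.02 | 0.93–0.97 |
| 0.05 | 0.87–0.94 |
| 0.10 | 0.80–0.90 |

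**Both problems together**, in the same runs without a cutoff: 0.88–0.97, 0.82–0.91 and 0.77–0.86 at 0.02, 0.05 and 0.10.

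**After correction.** With time ended at the matched window and at first event, simulated incidence ratios were 0.99–1.01. Late vorinostat-related events were not simulated in that check.

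**The case against.** The mismatch is narrower than it may sound. A subject who does not cross over and has no alternative therapy, death or cutoff within 90 days gets the right number of days. For crossovers, the denominator agrees with the main TEAE rule; only the exception for late vorinostat-related events lacks matching time. That exception may be rare in these four organ classes: the common vorinostat events in Protocol 8.2.3 are mostly of other kinds, and Protocol 5.3 normally requires toxicity to settle before crossover. All of this stands, and the 12% and 30% figures are illustrations within the crossover group only.

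Subjects with events over total time is also a known crude measure, the SAP states it openly, and each incidence table has an event-rate table beside it that is free of the first-event problem. Single preferred terms usually have low hazards, where the distortion is 1–7%; the larger figures suit common events or a whole organ class. This limits the size. It does not make the crude measure a remedy for unequal exposure, and the event rates still share the window mismatch.

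Finally, month 36 is not a fixed cutoff, because SAP 6.3 allows analysis up to 24 months after the last subject's first dose. The return to 1.00 after correction also relies on a constant hazard. Both points stand as limits on the illustration. Neither alters the disagreement between SAP 6.12.1 and the footnote.

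**Conclusion.** The concern holds, and the plan should be changed. The window mismatch follows from the text without any assumption: numerator and denominator follow different rules within one SAP. Its net direction cannot be stated, because the crossover and alternative-therapy shares are not given. In the equal-share scenarios with half starting alternative therapy, and from the cutoff alone, the effect is about 2–5%.

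The missing stop at first event affects only the four incidence tables. It has a predictable direction: the arm treated for longer looks better. The distortion is 1–2% at 0.005 per month and 10–20% at 0.10 per month, given equal constant hazards and treatment times set to the planned PFS medians.

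The tables are descriptive, no decision rule uses them, and the primary PFS analysis is unaffected. The practical weight is modest.

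**What to change.** 1. **Days at risk, both rates.** For subjects who do not cross over, take the earliest of last dose + 90 days, start of alternative therapy, death and data cutoff, minus first dose + 1. For crossovers, end on the day before the first KW-0761 dose; this gives the same number of days as the present footnote.
2. **Events.** In these rates, count only TEAEs with onset inside that window. Report later vorinostat-related AEs separately, and note that the rate numerators can then differ from the n (%) column and from Table 14.3.1.2.
3. **Incidence rates only.** Also end each subject's time at first onset of the organ class or preferred term being tabulated. Event rates keep the full matched window.
4. **Missing onset dates.** SAP 8.2.4 treats some AEs without a start date as treatment-emergent. State how they are placed in the window.
5. **Event-rate tables.** Table 14.3.3.3 repeats the note that counts a subject once, next to a formula that counts all AEs. State which columns the note governs.

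The cost is a change to SAP footnotes and programming. The dates are already collected: Listing 16.2.6.37 carries new therapy and death, and SAP 6.11.1.1 already uses the new-therapy date to censor PFS. Nothing changes for sites or subjects.

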2.2 Secondary Objectives

The secondary objectives will be:

- To compare the overall response rate of KW-0761 versus vorinostat in subjects with relapsed or refractory CTCL;
- To evaluate and compare improvements in QoL measurements, Skindex-29, FACT-G and EQ-5D-3L for subjects receiving KW-0761 versus vorinostat;
- To evaluate and compare improvements in the Pruritus Evaluation (Likert scale & Itchy QoL) for subjects receiving KW-0761 versus vorinostat;
- To estimate the duration of response for both the KW-0761 and vorinostat arms for those subjects with relapsed or refractory CTCL responding to treatment;
- To determine if subjects who relapse on vorinostat can achieve response upon cross over to treatment with KW-0761;
- To further assess the safety of KW-0761;
- To describe the immunogenicity of KW-0761.

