6.14 Analysis of Immunogenicity Data

[figure not shown]
Samples to detect anti-KW-0761 antibodies for the analysis of immunogenicity will be taken at baseline (Cycle 1, Day 1), Day 26-28 of Cycle 1, every 8 weeks thereafter, and at the end of treatment.

Anti-KW-0761 antibody status (positive, negative, and inconclusive) will be tabulated at each scheduled time point and overall at post-baseline for subjects in the KW-0761 arm and separately for those subjects who are randomized to vorinostat but crossed over into the KW-0761 arm. Anti KW-0761 antibody status will be determined using anti-KW-0761 antibody assay result and KW-0761 concentration value as outlined below:

- Positive: When the sample is positive in both screening assay and confirmatory assay, the sample status is considered to be Positive.
- Negative: When the sample is negative in screening assay and KW-0761 concentration at the same time point is equal to or less than drug tolerance limit (16000 ng/mL), or when the sample is positive in screening assay and negative in confirmatory assay, the sample status is considered to be Negative.
- Inconclusive: When the sample is negative in screening assay and KW-0761 concentration at the same time point is above the drug tolerance limit (>16000 ng/mL), the sample status is considered to be Inconclusive. When the sample is negative in screening assay and KW-0761 concentration is not measured, the sample status is considered to be inconclusive.

Anti KW-0761 Antibody Status

-decision tree-

The number and percentage of subjects with a positive neutralizing antibody test result will also be presented for each scheduled time point and overall at post-baseline. For each subject, overall is defined as positive if at least one post-baseline neutralization test result is positive.

Additionally, a summary of subjects with a positive overall assay at any time post-baseline and who experienced infusion reaction will be presented.

All immunogenicity data will be listed by subject.

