		>480 and <=500	xx (xx.x)	xx (xx.x)	xx (xx.x)	xx (xx.x)	xx (xx.x)
		>500	xx (xx.x)	xx (xx.x)	xx (xx.x)	xx (xx.x)	xx (xx.x)
		Total	xx (xx.x)	xx (xx.x)	xx (xx.x)	xx (xx.x)	xx (xx.x)

Note: Percentage is calculated using N' as the denominator, where N' is the number of subjects with both baseline and post baseline QTcB or QTcF measurements.

Table 14.3.7
 ECOG Performance Status Mean and Mean Change from Baseline by Selected Visits During Randomized Treatment Period
 Intent-to-Treat Set

Scale Time Point Statistic	Vorinostat (N=xx)			KW-0761 (N=xx)		
	Base	Post	Change	Base	Post	Change
ECOG Performance Status						
Baseline						
n	xx			xx		
Mean	xx.x			xx.x		
Std Dev	xx.xx			xx.xx		
Median	xx.x			xx.x		
Minimum	xx			xx		
Maximum	xx			xx		
End of Cycle 1						
n	xx	xx	xx	xx	xx	xx
Mean	xx.x	xx.x	xx.x	xx.x	xx.x	xx.x
Std Dev	xx.xx	xx.xx	xx.xx	xx.xx	xx.xx	xx.xx
Median	xx.x	xx.x	xx.x	xx.x	xx.x	xx.x
Minimum	xx	xx	xx	xx	xx	xx
Maximum	xx	xx	xx	xx	xx	xx
End of Cycle 3						
n	xx	xx	xx	xx	xx	xx
Mean	xx.x	xx.x	xx.x	xx.x	xx.x	xx.x
Std Dev	xx.xx	xx.xx	xx.xx	xx.xx	xx.xx	xx.xx
Median	xx.x	xx.x	xx.x	xx.x	xx.x	xx.x
Minimum	xx	xx	xx	xx	xx	xx
Maximum	xx	xx	xx	xx	xx	xx
Etc.						

<<Programming Note: Present for odd cycles.>>

Table 14.3.8.1
 Anti-KW-0761 Antibody Response
 Safety Analysis Set (Subjects Exposed to KW-0761)

Treatment Arm	Visit*	Anti-KW-0761 Antibody Status n/N' (%)			Neutralizing n/N' (%)
		Positive	Negative	Inconclusive ^{a)}	Positive
Initially Randomized to KW-0761 (N=xx)					
	Baseline	x/xx (xx.x)	x/xx (xx.x)	x/xx (xx.x)	x/xx (xx.x)
	End of Cycle 1	x/xx (xx.x)	x/xx (xx.x)	x/xx (xx.x)	x/xx (xx.x)
	End of Cycle x	x/xx (xx.x)	x/xx (xx.x)	x/xx (xx.x)	x/xx (xx.x)
	End of Cycle x	x/xx (xx.x)	x/xx (xx.x)	x/xx (xx.x)	x/xx (xx.x)
	.				
	.				
	EOT	x/xx (xx.x)	x/xx (xx.x)	x/xx (xx.x)	x/xx (xx.x)
	Overall	x/xx (xx.x)			
Crossed Over to KW-0761 (N=xx)					
	.				
	.				
All Subjects Exposed to KW-0761 (N=xx)					
	.				
	.				

* For subjects who cross over, the cycle number corresponds to the treatment cycle of KW-0761.
 a) Inconclusive because KW-0761 concentration is higher than drug tolerance limit (16000 ng/mL) or KW-0761 concentration is not determined.
 Note: Percentage is calculated using N' as the denominator, where N' is the number of subjects with valid measurements for anti-KW-0761 antibody at the specified visit. Overall is positive if at least one post-baseline assessment (including unscheduled) is positive.

Table 14.3.8.2

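### The overall anti-KW-0761 antibody result ignores baseline status, and has no stated denominator and no rule for calling a subject negative or inconclusive

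*SAP*

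**What the plan says.** Protocol 2.2 lists among the secondary objectives "To describe the immunogenicity of KW-0761".

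SAP 6.14 plans samples at "baseline (Cycle 1, Day 1), Day 26-28 of Cycle 1, every 8 weeks thereafter, and at the end of treatment". It classes each sample as positive, negative or inconclusive. A sample is positive when both the screening and the confirmatory assay are positive, at any drug concentration. A screen-negative sample is inconclusive if KW-0761 exceeds 16000 ng/mL, and also in this case: "When the sample is negative in screening assay and KW-0761 concentration is not measured, the sample status is considered to be inconclusive". The section then promises that "Anti-KW-0761 antibody status (positive, negative, and inconclusive) will be tabulated at each scheduled time point and overall at post-baseline".

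In Table 14.3.8.1 the three statuses are each printed as n over N' at every visit, and "N' is the number of subjects with valid measurements for anti-KW-0761 antibody at the specified visit". The inconclusive column carries the footnote "Inconclusive because KW-0761 concentration is higher than drug tolerance limit (16000 ng/mL) or KW-0761 concentration is not determined". The one rule for the Overall row is "Overall is positive if at least one post-baseline assessment (including unscheduled) is positive". For the neutralizing assay, SAP 6.14 uses the same form: "overall is defined as positive if at least one post-baseline neutralization test result is positive".

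**The concern.** The Overall row is the only place where the plan turns sample results into a subject-level result, so it is the figure most likely to be read as the immunogenicity incidence. Two things stop it from answering that question.

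- **Baseline is not used.** A pre-dose sample is taken and has its own table row, but the Overall rule never refers to it. Protocol exclusion criterion 11 bars prior KW-0761, so a positive baseline sample is pre-existing reactivity. If that subject is positive again after dosing, the rule counts an on-drug positive. No category separates antibody induced by treatment, antibody boosted by treatment, and reactivity that merely persisted.
- **The subject-level result is only half defined.** *Valid* is not explained and N' is tied to a visit. Nothing says when a subject is overall negative or overall inconclusive, although 6.14 promises all three statuses overall. The SAP does not accept a screen-negative sample above the drug tolerance limit as a negative, but that distinction has no counterpart at subject level.

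The any-post-baseline-positive rule also feeds Table 14.3.8.2, which relates antibody status to infusion reactions.

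**Working it through.** The plan states no antibody rate, inconclusive rate or baseline-positive rate, so there is no figure to reproduce. The check is a reading of the rules followed by an illustration on assumed inputs.

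**Reading the rules**

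1. At each visit Positive, Negative and Inconclusive share the denominator N'. A subject in the Inconclusive numerator must be in N', so inconclusive subjects are inside the visit denominators.
2. Overall is not a visit, so the definition of N' does not reach it. Carrying over the visit rows is the natural reading. Under it, a subject whose post-baseline samples are all inconclusive is in the denominator and not in the numerator.
3. A subject positive at baseline and at any later sample meets the Overall rule. A subject positive at baseline only does not.
4. The note to Listing 16.2.8.27 says that titer will be measured on positive samples. The information needed to recognise a boost is therefore planned, but no rule uses it.

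**Illustration (all counts assumed)**

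N' = 158, from the planned 317 subjects split 1:1 (317/2 = 158.5). P = 16 subjects with any positive post-baseline sample. I = subjects with only inconclusive post-baseline samples. B = subjects positive at baseline and again after baseline, none boosted.

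- Rule as written, visit denominator carried over: P/N' = 16/158 = 10.1%.
- Inconclusive subjects removed, P/(N' − I):
  - I = 8 (5%): 16/150 = 10.7%
  - I = 16 (10%): 16/142 = 11.3%
  - I = 40 (25%): 16/118 = 13.6%
  - I = 79 (50%): 16/79 = 20.3%
- Baseline positives removed, (P − B)/(N' − B):
  - B = 3 (2%): 13/155 = 8.4%
  - B = 8 (5%): 8/150 = 5.3%
- Both removed, (P − B)/(N' − I − B):
  - I = 8, B = 8: 8/142 = 5.6%
  - I = 40, B = 3: 13/115 = 11.3%
  - I = 79, B = 3: 13/76 = 17.1%

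Keeping the pre-existing subjects in the denominator, as the fix below does, changes little: with I = 40 and B = 3 it gives (16 − 3)/(158 − 40) = 13/118 = 11.0%, against 11.3%. If I and B are both zero, the printed rate is unchanged.

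**The case against.** The strongest reply is that this is a drafting gap in a descriptive output. No test, alpha or decision rule depends on it. Inconclusive counts by visit, the baseline row and the subject listing are all planned, so either rate can be derived later without new data. This stands, and it limits the weight of the point. It does not remove it, because the baseline omission is a stated rule and will be programmed as written.

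Four stronger readings are tempting, and the documents do not support them.

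- **A reader might infer that the Overall rate is defined over all tested subjects.** It is not defined. That denominator is an extension of the visit rows. Nor is the single filled cell in the shell's Overall row good evidence, since cells may have been lost when the table was extracted.
- **A reader might infer that every baseline-positive subject counts as positive.** A positive post-baseline sample is also required.
- **A reader might infer that most subjects will be inconclusive throughout, because the end-of-Cycle-1 sample follows four weekly doses.** The readable text gives no volume or half-life. Assume one compartment, volume 45–90 mL/kg, half-life 10–21 days and 40% between-subject variation. Then 59–100% of single samples exceed 16000 ng/mL at Cycle 1 Day 27, and 4–99% at the end of Cycles 3 and 5. A share of single samples is not a share of subjects inconclusive at every sample. There is also an end-of-treatment sample, and Protocol 7 places that visit within 30 days of the last dose. At mid-range values (65 mL/kg, 14 days; last dose on Day 15 of Cycle 3 or 5) the share above the limit is about 46–51% at 14 days after the last dose, 17–20% at 21 days and 2–3% at 30 days. These figures do not size the problem.
- **A reader might infer that positives over positives plus negatives is the correct rate.** Positives are accepted at any drug level, while screen-negatives above the limit are set aside. The denominator then depends partly on the outcome, and that rate alone can overstate incidence.

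**Conclusion.** The point holds as a defect in how the overall result is defined. For both assays the stated rule mixes persisting pre-existing reactivity with treatment-emergent antibody. For the antibody assay, the Overall denominator and the subject-level negative and inconclusive statuses are missing.

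A claim that the reported incidence is biased in a known direction would go too far. The two effects oppose each other, and the documents give neither the inconclusive rate nor the baseline-positive rate. The 5.6% to 17.1% span around a printed 10.1% rests wholly on the assumed counts and shows sensitivity only. The change is worth making because it is cheap and bears on a stated secondary objective. It has no bearing on PFS, the type I error rate or power.

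**What to change.** In SAP 6.14 and Table 14.3.8.1, give each exposed subject with a post-baseline sample exactly one overall antibody status:

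- **Treatment-induced positive:** baseline not positive, any post-baseline sample positive.
- **Treatment-boosted positive:** baseline positive, with a titer rise whose threshold is fixed in advance.
- **Pre-existing, not boosted:** baseline positive without such a rise. This needs its own row and must not be folded into Inconclusive.
- **Negative:** baseline not positive, no positive post-baseline sample, and at least one conclusive negative. The rule should say whether one early conclusive negative is enough when all later samples are inconclusive.
- **Inconclusive:** baseline not positive, no positive post-baseline sample and no conclusive negative.

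Report treatment-emergent incidence (induced plus boosted) over subjects with a conclusive status, with the inconclusive count beside it. Also give the rate over all tested subjects, because leaving out the inconclusive ones can overstate incidence. Define *valid* and state both denominators. For crossover subjects, use the last sample before the first KW-0761 dose as baseline, as SAP 6.2 already provides. Separate baseline-positive subjects in the same way for the neutralizing assay, and carry the statuses into Table 14.3.8.2.

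The cost is SAP text and table-shell edits. No new samples or assays are needed, provided titers are measured as the listing note says. The downside is a smaller denominator and possibly a less favourable rate.
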